6.14.5.13. Columbia Suicide Severity Rating Scale	80
6.14.5.13.1. Self-Harm Supplemental Form and Self-Harm Follow-up Form.....	81

6.15. Subgroup Analyses.....	81
6.16. Protocol Violations.....	82
6.17. Interim Analyses and Data Monitoring	82
6.17.1. Interim Analysis Plan.....	83
6.18. Planned Exploratory Analyses.....	84
6.19. Annual Report Analyses.....	84
6.20. Clinical Trial Registry Analyses	84
7. Unblinding Plan	85
8. References	86

Table of Contents

Table	Page
Table JAIW.6.1. Imputation Techniques for Various Variables	22
Table JAIW.6.2. Seed Values for Multiple Imputation	25
Table JAIW.6.3. Seed Values for Imputation.....	27
Table JAIW.6.4. Description and Derivation of Primary, Secondary, and Exploratory Efficacy Outcomes	36
Table JAIW.6.5. Description of Primary, Secondary and Exploratory Efficacy Analyses	40
Table JAIW.6.6. Description and Derivation of Health Outcomes and Quality-of-Life Measures	46
Table JAIW.6.7 Description of Health Outcomes and Quality-of-Life Measures Analyses	59
Table JAIW.6.8. Categorical Criteria for Abnormal Treatment-Emergent Blood Pressure and Pulse Measurement, and Categorical Criteria for Weight Changes for Adults	70

Table of Contents

Figure	Page
Figure JAIW.5.1. Illustration of study design for I4V-MC-JAIW.....	13
Figure JAIW.6.1. Illustration of graphical multiple testing procedure with initial α allocation and weights.	30

3. Revision History

Statistical Analysis Plan (SAP) Version 1 was based on Protocol I4V-MC-JAIW(a) and was approved prior to the first unblinding.

Statistical Analysis Plan Version 2 was based on Protocol I4V-MC-JAIW(c) and Program Safety Statistical Analysis plan (PSAP) Version 6. It was approved prior to Week 16 Database lock (DBL).

Statistical Analysis Plan Version 3 was based on Protocol I4V-MC-JAIW(c) and PSAP Version 6. It was approved prior to 4 month safety DBL. It included the following updates:

- Add timepoint Week 40 (Visit 10), Week 64 (Visit 12), Week 76 (Visit 13), Week 88 (Visit 14) for some efficacy/health outcome endpoints as exploratory analyses
- Define the patient analysis population for Week 16 responders

Statistical Analysis Plan Version 4 was based on Protocol I4V-MC-JAIW(c) and Program Safety PSAP Version 7. It was approved prior to the final DBL. It included the following updates:

- Sections 4.2 (Secondary Objectives) and 4.3 (Exploratory Objectives): specified the timepoints for the other secondary objectives and exploratory objectives analyses. Removed some repeated summaries from Section 4.3 as they are in Section 4.2 already.
- Section 6.2 (Generation Considerations): at the last sentence, classified the usage for the unscheduled visit data for safety analytes.
- In the end of Section 6.2.4 (Analysis Methods), added a statement about the long-term efficacy and safety analyses that will be evaluated in combination of Studies I4V-MC-JAIW and I4V-MC-JAIX.
- Section 6.2.2 (Analysis Populations): clarified the population set for the final DBL (it will use Week 16 responders population).
- Section 6.2.3 (Definition of Baseline and Postbaseline Measures): Under the Postbaseline sub-section, add the definition for Postbaseline measurements.
- Section 6.4 (Handling of Dropouts or Missing Data) and Table 6.1 (Imputation Techniques for Various Variables): added modified last observation carried forward for categorical response endpoints.
- Section 6.7 (Patient Disposition): added the summary for the final DBL.
- Section 6.9 (Treatment Compliance): added the summary for the final DBL.
- Section 6.14 (Safety Analyses): revised treatment-emergent adverse event definition for Week 16 responders final DBL and added the scope of summary for the safety part in the final DBL.

4. Study Objectives

4.1. Primary Objective

The primary objective of this study is to test the hypothesis that baricitinib 2-mg once daily (QD) is superior to placebo in the treatment of patients with moderate to severe atopic dermatitis (AD), as assessed by the proportion of patients achieving EASI75 at Week 16.

The associated estimand for this objective is to measure the effect of baricitinib therapy as assessed by the proportion of patients achieving EASI75 at Week 16 assuming the treatment response disappears after patients are rescued or discontinue from study or treatment. See also Sections 6.4 and 6.4.1 on how this estimand handles outcomes after occurrence of any intercurrent event through non-responder imputation (NRI).

4.2. Secondary Objectives

4.2.1. Key Secondary Objectives

These are prespecified objectives that will be adjusted for multiplicity.

Objective	Endpoint
To compare the efficacy of baricitinib 1-mg once daily (QD) or 2-mg QD to placebo in atopic dermatitis (AD) during the 16-week double-blind placebo-controlled treatment period as measured by improvements in signs and symptoms of AD.	
 Proportion of patients achieving Investigator's Global Assessment (IGA) of 0 or 1 with a ≥ 2-point improvement at Week 16 Proportion of patients achieving 75% improvement from baseline using the Eczema Area and Severity Index score (EASI75) at Week 16 (1-mg) Proportion of patients achieving 90% improvement from baseline using the Eczema Area and Severity Index score (EASI90) at Week 16 Mean percent change from baseline in EASI score at Week 16 Proportion of patients achieving SCORing Atopic Dermatitis (SCORAD75) at Week 16
To compare the efficacy of baricitinib 1-mg QD or 2-mg QD to placebo in AD during the 16-week, double-blind, placebo-controlled treatment period as assessed by patient-reported outcome measures	
 Proportions of patients achieving a 4-point improvement in Itch Numeric Rating Scale (NRS) at 1 week, 2 weeks, 4 weeks, and 16 weeks Mean change from baseline in the score of Item 2 of the Atopic Dermatitis Sleep Scale (ADSS) at 1 week and 16 weeks Mean change from baseline in Skin Pain NRS at Week 16

4.2.2. Other Secondary Objectives

These are prespecified objectives that will not be adjusted for multiplicity.

Objective	Endpoint
To compare the efficacy of baricitinib 1-mg QD or 2-mg QD to placebo in AD during the 16-week, double-blind, placebo-controlled period as measured by improvement in signs and symptoms of AD	
 Proportion of patients achieving Investigator's Global Assessment (IGA) of 0 or 1 with a ≥ 2-point improvement at Week 4 Proportion of patients achieving 50% improvement from baseline using the Eczema Area and Severity Index score (EASI50) at Week 16 Proportion of patients achieving IGA of 0 at Week 16 Mean change from baseline in SCORing Atopic Dermatitis (SCORAD) at Week 16 Proportion of patients achieving SCORAD90 at Week 16 Mean change from baseline in body surface area affected at Week 16 Proportion of patients developing skin infections requiring antibiotic treatment by Week 16
To compare the efficacy of baricitinib 1-mg QD or 2-mg QD to placebo in AD during the 16-week, double-blind, placebo-controlled treatment period as assessed by patient-reported outcome/quality of life (QoL) measures	
 Mean percent change from baseline in Itch Numerical Rating Scale (NRS) at 1 week and 16 weeks Mean change from baseline in Itch NRS at 4 weeks and 16 weeks Mean change from baseline in the total score of the Patient-Oriented Eczema Measure (POEM) at Week 16 Mean change in Patient Global Impression of Severity (PGI-S-AD) scores at Week 16 Mean change from baseline in the Hospital Anxiety Depression Scale (HADS) at Week 16 Mean change in Dermatology Life Quality Index (DLQI) scores at Week 16 Mean change in Work Productivity and Activity Impairment: Atopic Dermatitis (WPAI-AD) scores at Week 16 Mean change in European Quality of Life-5 Dimensions-5 Levels (EQ-5D-5L) scores at Week 16

4.2.3. Other Secondary Objectives for Week 16 Responders

The secondary objectives and corresponding endpoints for those who responded at Week 16 and continue in the study beyond 16 weeks are as follows:

Objective	Endpoint
To describe the long-term efficacy of baricitinib 1-mg QD or 2-mg QD in AD as measured by improvement in signs and symptoms of AD	
 Proportion of patients with a response of Investigator's Global Assessment (IGA) 0 or 1 at Week 16 who maintain an IGA 0 or 1 at Weeks 28, 40, 52, 64, 76, 88 and 104 Proportion of patients with a response of IGA 0 or 1 at Week 16 who achieve Eczema Area and Severity Index score (EASI75) assessed at Weeks 28, 40, 52, 64, 76, 88 and 104 Proportion of patients with a response of IGA 0 or 1 at Week 16 who achieve SCORing Atopic Dermatitis (SCORAD75) at Weeks 28, 40, 52, 64, 76, 88 and 104 Mean percent change from baseline in EASI score at Weeks 28, 40, 52, 64, 76, 88 and 104 Mean percent change from baseline in SCORAD score at Weeks 28, 40, 52, 64, 76, 88 and 104 Mean percent change from baseline in SCORAD pruritus at Weeks 28, 40, 52, 64, 76, 88 and 104 Mean percent change from baseline in Patient Oriented Eczema Measure (POEM) at Weeks 28, 40, 52, 64, 76, 88 and 104

4.3. Exploratory Objectives

The exploratory objectives of this study are as follows:

Objective

Exploratory objectives evaluating the response to baricitinib treatment regimens on other patient reported outcomes may include dichotomous endpoints or change from baseline for the following measures: Patient-Oriented Eczema Measure (POEM), Dermatology Life Quality Index (DLQI), Itch Numerical Rating Scale (NRS), Atopic Dermatitis Sleep Scale (ADSS), Skin Pain NRS, Hospital Anxiety Depression Scale (HADS), Eczema Area and Severity Index score (EASI) and SCORing Atopic Dermatitis (SCORAD). Topical corticosteroids(TCS) use will be explored.
 
 Time to First Eczema Area and Severity Index score (EASI) 75% Reduction Response by Week 16 Time to First Investigator's Global Assessment IGA (0,1) Response by Week 16 Time to First Itch 4 point reduction Response by Week 16 Proportions of patients achieving a Skin pain 4-pt improvement for those with baseline Skin pain ≥ 4 by Week 16 Proportions of patients achieving a DLQI 4-pt improvement for those with baseline DLQI ≥ 4 by Week 16 Proportions of patients achieving a DLQI 5 score or less for those with baseline DLQI > 5 Proportions of patients achieving a DLQI 0 or 1 by Week 16 Proportions of patients achieving a POEM 4-pt improvement for those with baseline POEM ≥ 4 by Week 16 Proportions of patients achieving a HADS Anxiety < 8 for those with baseline HADS A ≥ 8 by Week 16 Proportions of patients achieving a HADS Depression < 8 for those with baseline HADS D ≥ 8 by Week 16 Proportions of patients achieving a HADS A or HADS D < 8 for those with baseline HADS A ≥ 8 or HADS D ≥ 8 by Week 16

Objective

• HADS total score change from baseline using mixed model repeated measures (MMRM) by Week 16• Proportions of patients achieving a ADSS2 1.5-pt improvement for those with baseline ADSS2 ≥ 1.5 by Week 16• Mean change from baseline in the score of Item 1 of the ADSS at 1 week and 16 weeks• Mean change from baseline in the score of Item 3 of the ADSS at 1 week and 16 weeks• Mean change from baseline in EASI score at Week 16• Mean percentage change from baseline in SCORing Atopic Dermatitis (SCORAD) score at Week 16• Proportions of patients achieving a DLQI 5 score or less for those with baseline DLQI > 5 at Weeks 28, 40, 52, 64, 76, 88 and 104• Mean change from baseline in DLQI score at Weeks 28, 40, 52, 64, 76, 88 and 104

[figure not shown]
5. Study Design

Study I4V-MC-JAIW (JAIW) is a multicenter, randomized, double-blind, placebo-controlled, parallel-group, outpatient Phase 3 study evaluating the efficacy and safety of baricitinib 1-mg QD and 2-mg QD as compared to placebo in adult patients with moderate to severe AD. The study is divided into 3 periods: a 5-week Screening Period, a 104-week Double-Blinded Treatment Period, and a 4-week Post-Treatment Follow-Up Period.

Approximately 450 patients aged ≥ 18 years who have responded inadequately to or who are intolerant of topical therapy will be randomized at a 1:1:1 ratio to receive placebo QD, baricitinib 1-mg QD, or baricitinib 2-mg QD (approximately 150 patients per group). Patients will be stratified at randomization according to disease severity (IGA 3 versus 4).

The primary and key secondary endpoints are assessed prior to or at Visit 8 (Week 16). At Week 16 those patients who met IGA 0 or 1 and who have not required rescue therapy prior to Week 16 will be allowed to continue in this study. All other patients will be discontinued from this study and may be eligible to enroll in a separate open-label study (Study JAIX). Patients experiencing worsening in disease severity resulting in an IGA score of ≥ 3 after Week 16 of Study JAIW will also have to be discontinued from this study and may be eligible to enroll in the open-label Study JAIX. Patients who complete Week 104 (Visit 15) will have the option to transition to open-label Study JAIX, if eligibility criteria are met regardless of responder status, or continue to the post-treatment follow-up.

Figure JAIW.5.1 illustrates the study design.

Abbreviations: AD = atopic dermatitis; QD = once daily; V = visit; W = week.

- ^a At Week 16, all patients who achieve an IGA 0 or 1 and who have not required rescue therapy before Week 16 will be allowed to continue in this study. All other patients will be discontinued from this study and may be eligible to enroll in the separate open-label Study JAIX.
- ^b Patients who complete this study will be eligible for assessment to enroll in open-label Study JAIX.
- ^c Occurs approximately 28 days after the last dose of investigational product.

Figure JAIW.5.1. Illustration of study design for I4V-MC-JAIW.

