Hospital Anxiety Depression Scale (HADS)	
The HADS is a 14-item self-assessment scale that determines the levels of anxiety and depression that a patient is experiencing over the past week. The HADS utilizes a 4-point Likert scale (eg, 0 to 3) for each question and is intended for ages 12 to 65 years (Zigmond and Snaith 1983; White et al. 1999). Scores for each domain (anxiety and depression) can range from 0 to 21, with higher scores indicating greater anxiety or depression (Zigmond and Snaith 1983; Snaith 2003).
	HADS score for anxiety and depression domains	Anxiety domain score is sum of the seven anxiety questions, range 0 to 21. Depression domain score is sum of the seven depression questions, range 0 to 21.	N/A – partial assessments cannot be saved.
		Change from baseline in HADS domain	Change from baseline: observed HADS domain score – baseline HADS domain score	Missing if baseline or observed value is missing.
		Change from baseline in HADS total	Change from baseline: observed HADS domain score – baseline HADS total score	Missing if baseline or observed value is missing.
		
 ▪ HADS Anxiety <8 in subgroup of patients with baseline HADS Anxiety score ≥ 8 ▪ HADS Depression <8 in subgroup of patients with baseline HADS Depression score ≥ 8 	observed HADS postbaseline <8 and baseline score ≥ 8 for each HADS domain score	Missing if baseline is missing or <8 or observed value is missing.

Description and Derivation of Health Outcomes and Quality-of-Life Measures

Measure	Description	Variable	Derivation/Comment	Imputation Approach if with Missing Components
Hospital Anxiety Depression Scale (HADS)	The HADS is a 14-item self-assessment scale that determines the levels of anxiety and depression that a patient is experiencing over the past week. The HADS utilizes a 4 point Likert scale (eg, 0 to 3) for each question and is intended for ages 12 to 65 years (Zigmond and Snaith 1983; White et al. 1999). Scores for each domain (anxiety and depression) can range from 0 to 21, with higher scores indicating greater anxiety or depression (Zigmond and Snaith 1983; Snaith 2003).	
 ▪ HADS Anxiety or Depression score <8 in subgroup of patients with baseline HADS Anxiety or Depression score ≥ 8 	observed HADS postbaseline <8 and baseline score ≥ 8 for any HADS domain score	Missing if baseline is missing or <8 or observed value is missing for both domain

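### The combined HADS responder endpoint is defined inconsistently: its label lets patients with one elevated domain respond at baseline, while its derivation most naturally does not

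*SAP*

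**What the plan says.** The combined HADS endpoint appears in four statements.

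- **Section 4.3, Exploratory Objectives:** the response clause is "Proportions of patients achieving a HADS A or HADS D < 8"; with the baseline subset attached, the endpoint reads "Proportions of patients achieving a HADS A or HADS D < 8 for those with baseline HADS A ≥ 8 or HADS D ≥ 8".
- **Table JAIW.6.6 (Section 6.12), variable label:** "HADS Anxiety or Depression score <8 in subgroup of patients with baseline HADS Anxiety or Depression score ≥ 8".
- **Table JAIW.6.7 (Section 6.12), analysis entry:** the same label, analysed at Week 16 in the ITT population by logistic regression with non-responder imputation, each dose against placebo, marked exploratory.
- **Table JAIW.6.6, derivation cell:** "observed HADS postbaseline <8 and baseline score ≥ 8 for any HADS domain score". The missing-data cell beside it reads "Missing if baseline is missing or <8 or observed value is missing for both domain".

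For comparison, the derivation of the two single-domain endpoints in Table JAIW.6.6 is "observed HADS postbaseline <8 and baseline score ≥ 8 for each HADS domain score". Each domain score runs from 0 to 21. Section 6.11.2 places everything beyond the primary and key secondary endpoints outside multiplicity adjustment.

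**The concern.** The objective and the two labels use *or* twice, once for who enters the subset and once for who responds. Nothing in them links the domain that qualified the patient to the domain that must fall below 8. A patient who enters through one elevated domain meets the response criterion through the other, which was never elevated. The derivation cell appears to supply the missing link, but it does not say so outright, and if it does supply it, it contradicts its own label.

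Table JAIW.6.7 plans a between-arm comparison on this endpoint. Two programmers working from different lines of the SAP could report different response rates and different treatment effects. Under the literal rule, part of the response rate in every arm would have nothing to do with treatment.

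**Working it through.** The SAP gives no figure for this endpoint, so there is none to reproduce. The check is one of logic, followed by an illustration of size.

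**Step 1. The candidate rules**, all in patients with A ≥ 8 or D ≥ 8 at baseline:

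- *Literal* (Section 4.3 and both labels): A < 8 or D < 8 at Week 16.
- *Same domain, any* (natural reading of the derivation cell): at least one domain goes from ≥ 8 to < 8.
- *Every elevated domain*: each domain ≥ 8 at baseline is < 8 at Week 16.
- *Both below*: A < 8 and D < 8 at Week 16.

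**Step 2. The rules applied to example patients**

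| Baseline (A, D) | Week 16 (A, D) | Literal | Same domain, any | Every elevated domain | Both below |
|---|---|---|---|---|---|
| 12, 4 | 12, 4 | yes | no | no | no |
| 15, 15 | 15, 15 | no | no | no | no |
| 15, 15 | 15, 7 | yes | yes | no | no |
| 12, 4 | 7, 12 | yes | yes | yes | no |

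Row 1 is the conflict: no change at all, yet a responder under three of the SAP's statements and a non-responder under the fourth. Row 3 shows that same-domain pairing still counts a patient whose anxiety stays elevated. Row 4 separates the last two rules.

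**Step 3. All possible unchanged scores.** With each domain an integer from 0 to 21, 14 values are ≥ 8 and 8 values are < 8.

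- One domain elevated: 2 × 14 × 8 = 224 score pairs.
- Both elevated: 14 × 14 = 196 score pairs.

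With scores unchanged from baseline, the literal rule makes all 224 single-elevated pairs responders and none of the 196 both-elevated pairs. Under *same domain, any* and under *both below*, the counts are 0 of 224 and 0 of 196. These count possible score pairs, not patients.

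**Step 4. Illustration of dilution.** None of these inputs is in the SAP; all are assumed. An elevated domain normalises with probability q = 0.30 on placebo and 0.45 on drug. The domains are independent. In single-elevated patients the other domain rises to ≥ 8 with probability w = 0.05 to 0.15. A share s of the subset is single-elevated.

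- Literal rate = s[1 − (1 − q)w] + (1 − s)[1 − (1 − q)²]
- Same-domain rate = s·q + (1 − s)[1 − (1 − q)²]

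For s = 0.5 and w = 0.05:

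- Literal, placebo: 0.5 × 0.965 + 0.5 × 0.51 = 0.738
- Literal, drug: 0.5 × 0.9725 + 0.5 × 0.6975 = 0.835
- Literal difference: 9.7 points
- Same domain, placebo: 0.5 × 0.30 + 0.5 × 0.51 = 0.405
- Same domain, drug: 0.5 × 0.45 + 0.5 × 0.6975 = 0.574
- Same-domain difference: 16.9 points

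| s | Literal difference, w = 0.05 | Literal difference, w = 0.15 | Same-domain difference |
|---|---|---|---|
| 0.3 | 13.4 points | 13.8 points | 17.6 points |
| 0.5 | 9.7 points | 10.5 points | 16.9 points |
| 0.7 | 6.1 points | 7.2 points | 16.1 points |

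Over the same range, the placebo response rate is 62.5% to 82.9% under the literal rule and 36.3% to 44.7% under same-domain pairing.

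**The case against.** The best defence is that Table JAIW.6.6 is where the SAP puts its derivations, and that its derivation cell governs. That cell joins the baseline and post-baseline conditions, in parallel with the single-domain row above it. The missing-data cell points the same way: a domain below 8 at baseline is treated as not evaluable, and the patient is missing only if that holds for both domains. On this reading the patient with Anxiety 12 and Depression 4 is judged on Anxiety alone and is not a responder at baseline. This is the more natural reading of the cell, and the argument stands as far as it goes. It does not settle the matter. The cell never states that the two conditions apply to one domain, and the objective and both labels say something else.

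It is also fair to say that counting a patient as a responder when any elevated domain normalises is a coherent definition. Requiring both domains below 8 is stricter and is one acceptable choice, not the only correct one. The SAP does not say which was meant.

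A reader might infer that the endpoint cannot measure response at all. The documents do not support that, even on the literal reading. Patients elevated on both domains do not respond at baseline, and the contrast is weakened, not lost. Nor do the documents show what share of patients would be baseline responders, because they do not say how many have only one elevated domain.

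**Conclusion.** The point holds as an inconsistency in the definition. Section 4.3 and the labels in Tables JAIW.6.6 and JAIW.6.7 give a rule that every single-elevated patient already meets at baseline. The derivation cell most naturally gives a different rule, which avoids this but leaves the pairing unstated and accepts a patient whose other domain stays elevated.

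If the literal rule were programmed, response rates would be inflated in all arms and the treatment difference diluted. The illustration suggests a loss of roughly 4 to 10 points from a difference of 16 to 18, depending on the single-elevated share. That range rests entirely on assumed rates, on independence of the domains and on no missing data. If same-domain pairing were programmed, there would be no inflation at baseline.

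The consequence for the trial is low. The endpoint is exploratory and outside the multiplicity procedure. It sits beside separate Anxiety and Depression responder endpoints, which are correctly paired, and beside MMRM analyses of the domain and total scores.

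**What to change.** State one response rule in identical words in Section 4.3, in Table JAIW.6.6 (label and derivation) and in Table JAIW.6.7, for patients with at least one domain ≥ 8 at baseline. Either of these is suitable:

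- every domain that was ≥ 8 at baseline is < 8 at Week 16; or
- both A < 8 and D < 8 at Week 16.

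The second also excludes a patient whose other domain newly crosses 8. If the sponsor intends that any one elevated domain normalising is enough, the text should say explicitly that the same domain must go from ≥ 8 to < 8.

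Change only the response clause. The *or* that defines the baseline subset is right and should stay. Check that the missing-data cell matches the rule chosen.

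The cost is a few words in each place, with no new data. Section 6.2.1 records that the Week 16 lock has been executed, so the report should also state which rule was programmed and, if it was the literal one, add the result under the chosen rule.
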